#### 4.3 Eligibility Criteria

Patients are required to meet ALL the following criteria in order to be included in this study:

#### 4.3.1 Inclusion Criteria

- 1. Patient is age  $\geq$ 18 and  $\leq$ 85 years at date of consent.
- 2. Patient has provided written informed consent for participation in the study prior to index procedure.
- Patient has documented symptomatic peripheral arterial disease scheduled for treatment with the BioMimics 3D stent in accordance with the approved CE indication and Instructions for Use (IFU)

### 4.3.2 Exclusion Criteria

- 1. Patients whose lesions cannot be crossed with a wire and/or balloon catheter and cannot be dilated sufficiently to allow passage of the delivery system.
- 2. Patients with a history of intolerance or adverse reaction to antiplatelet and/or anticoagulation therapies, bleeding diathesis, severe hypertension or renal failure.
- 3. Patients with known hypersensitivity to nickel-titanium.
- 4. Patient has a comorbidity that in the Investigator's opinion would limit life expectancy to less than 12 months.
- 5. Patient is pregnant or breastfeeding.
- 6. Patient is unable or is unwilling to comply with site standard of care procedures and follow-up visit schedules for patients undergoing femoropopliteal intervention.

#### 5.0 SCREENING AND ENROLMENT

#### 5.1 Screening

All consecutive patients who meet the eligibility criteria should be considered for enrolment in the study. Sites should maintain a cumulative log of all enrolled patients. The Investigator or designee should

determine potential eligibility according to Section 4.3. Patients who meet all criteria should be provided with further information on the study in accordance with the procedures in Section 5.2.

### 5.2 Informed Consent

Written Consent for Data Collection with the Ethics Committee (EC)/Institutional Review Board (IRB) approved consent form will be obtained for all patients prior to Study procedure and collection of any Study-specific information. There are no additional procedures or tests required in addition to routine standard of care.

The patient shall be given adequate time to read the Written Consent for Data Collection consent form and have the data collection and data transmission procedures explained prior to signing the Informed Consent form. All patients providing informed consent for data collection are to receive copies of their signed informed consent documentation. The consent process may be obtained up to 30 days prior to enrolment in the Study.

### 5.3 Enrolment

All patients who provide written informed consent for the Study, meet all eligibility criteria and are treated with BioMimics 3D stent system will be considered enrolled in the Study. If the BioMimics 3D Stent System is inserted into the vasculature and treatment is attempted, but the procedure is aborted without delivery of a stent, only device failure and malfunction information and/or device related adverse events should be collected, if applicable.

Patients who are consented but the BioMimics 3D Stent System is not inserted into the vasculature will be considered screen failures. No data will be collected on screen failures.

Patients who are enrolled and treated, but who are later discovered to not meet all of the eligibility criteria will remain in the Study for follow-up and a Protocol Deviation form will be completed.

Patients who are enrolled and undergo staged treatment using BioMimics 3D Stent System in both limbs will be considered a single enrolment. Procedural information for both limbs will be collected.

For the purpose of this study, the point of enrolment is time of index procedure.

### 5.4 Withdrawal

Patients may withdraw at any time from the Study without prejudice; participation is entirely voluntary. If a subject prematurely terminates from the Study, the reason for termination will be recorded in the eCRF.

The Investigator should follow all unresolved serious adverse events until the events are resolved, the subject is lost to follow-up, the subject has withdrawn consent, the subject completes the Study follow-up, or the adverse event is otherwise explained.

All reasonable efforts will be made to obtain complete data for all subjects; however, missing observations will occur due to loss to follow-up, withdrawal, or variation in site standard of care assessments. Site shall make all reasonable efforts to contact subjects who do not respond to follow-up requests. In the event patient does not respond to a final contact attempt via certified letter, patient will be considered lost to follow-up. Patients who withdraw consent after treatment will have their data evaluated until the time of their withdrawal (unless consent for data retention is removed in accordance with local or national regulations). Patients who withdraw or are lost to follow-up will not be replaced.

### 6.0 DATA COLLECTION PROCEDURES

### 6.1 Visit Schedule

Study participation will last for a total of 36 months ( $\pm$  60 days). Data collection will be completed at baseline index hospitalisation, 30 days ( $\pm$  7 days), 12 months (365 days  $\pm$  30 days), 24 months (730 days  $\pm$  60 days) and 36-months (1095 days  $\pm$  60 days). Follow-up may be by clinic visit or telephone according to site standard of care.

A summary schedule of the data collection for tests and evaluations is in Table 1. Data should only be collected if tests and evaluations are completed per standard of care.

### Table 1: Data Collection Schedule

Assessment	Baseline	Day 0 Index Procedure (Enrolment / Treatment)	Follow-up Visits 30 days (± 7 days), 12 months (365 days ± 30 days), 24 months (730 days ± 60 days), 36-months (1095 days ± 60 days)
Informed Consent	Х	-	
Medical History	х		х
ABI/TBI	X		х
Rutherford Clinical Category (RCC)	Х		х
Procedural data & technical success		X**	
Index procedure angiographic assessments		х	
Follow-up standard of care imaging assessments, as applicable: • Angiography • Duplex ultrasound • X-ray			х
Concomitant antiplatelet and anticoagulant medications	х	х	Х
Adverse Event Assessment		х	х
Subsequent intervention (target limb)		×	х
Device use questionnaire (operator)		Х	
Walking Impairment Questionnaire (WIQ)*	0		0

\*WIQ is optional (O) and may be collected if standard of care at site.

\*\* Females of childbearing potential should have a negative pregnancy test before procedure (according to site standard of care)

### 6.2 Baseline

The following baseline data will be collected:

- Demographic information (age at time of treatment/enrolment, sex, ethnicity)
- Relevant medical history including previous peripheral interventions and cardiovascular risk factors
- Physical examination (as available)
  - o Height and weight
  - Ankle Brachial Index (ABI) or Toe Brachial Index (TBI) (if applicable)
  - Rutherford Clinical Category
- Concomitant antiplatelet and anticoagulant medication

### 6.3 Index Procedure

All procedures should be conducted in accordance with site standard of care and patient needs, there are no prohibited concomitant treatments. BioMimics 3D stent deployment shall be conducted in accordance with the IFU.

Data will only be collected on patients who have provided their consent and are treated, or treatment is attempted with BioMimics 3D stent system. All other patients will be considered screen failures and no data will be collected.

The following data will be collected at index procedure through to discharge:

- Lesion pre-treatment, e.g., PTA, drug-eluting balloon therapy, atherectomy, laser
- Baseline angiographic assessment, i.e., lesion size, inflow and outflow disease
- Stent placement: location, size and lot number/expiry of stent(s)
- Post-stenting treatment
- Assessment of final lumen patency via angiogram at the conclusion of the index procedure (percent angiographic stenosis)

- Procedure time
- Concomitant peripheral procedures
- Adverse events and device observations
- Device use questionnaire (completed by operator)
- Concomitant antiplatelet and anticoagulant medication

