### 3.0 STUDY PLAN

#### 3.1 Study Objective

The MIMICS-3D Study will evaluate safety, effectiveness and device performance within a real-world clinical population of patients undergoing femoropopliteal intervention.

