### 4.2 Secondary Outcome Measures

• Acute technical success defined as the achievement of a final residual diameter stenosis <30% at the end of the procedure

- Acute procedural success defined as both acute technical success and absence of the following adverse events: death, stroke, MI, acute onset of limb ischemia, index bypass graft or treated segment thrombosis, and/or need for urgent/emergent vascular surgery, within 72 h of the index procedure.
- Incidence of individual components of MAE (death, any major amputation performed on the index limb or CDTLR) at 30 days, 12, 24 and 36 months
- Overall rate and incidence of adverse events from Day 0 through completion of study follow-up at Month 36.
- Stent patency rate assessed by duplex ultrasound, as available, determined at Months 12, 24 and 36. This will be assessed using values of PSVR >2.0, >2.4; >2.5; and >3.5 each to indicate loss of patency on duplex ultrasound.
- Clinical outcome: comparison of Rutherford Clinical Category measured at Baseline, Day 30, Months 12 24 and 36.
- Functional outcome: comparison of the ankle brachial index (ABI) measurement at Baseline, within 30 days after index procedure, then at Months 12, 24 and 36.
- Incidence of reported stent fractures through 36 months.
- Operator assessment of device use

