### 9.1 Analysis Population

- Intention-to-Treat (ITT) Analysis Set: includes all enrolled subjects.
- *Modified Intention-to-Treat (mITT) Analysis Set*: includes all enrolled subjects in whom the BioMimics 3D Stent System is implanted. Those subjects in whom the procedure is aborted without implantation of a stent will be excluded from this analysis set. This is the primary

analysis set for the primary safety and effectiveness endpoints, as well as secondary and exploratory endpoints.

• *Per-Protocol (PP) Analysis Set:* includes all enrolled subjects in whom the BioMimics 3D Stent System is implanted and who met all inclusion/exclusion criteria with no major protocol deviations. Those subjects in whom the procedure is aborted without implantation of a stent will be excluded from this analysis set. This is a secondary analysis set for the primary safety and effectiveness endpoints, as well as secondary endpoints.

While mITT is intended as the primary analysis set for all safety and effectiveness endpoints, the primary safety and effectiveness endpoints will additionally be evaluated in the ITT and PP analysis sets as supportive information. All subjects excluded from mITT analysis set will be described and the reasons for aborted procedures, if any, detailed.

A separate analysis will be conducted for the DCB cohort.

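### Acute technical success credits the study stent with results rescued by a non-study stent in the same lesion, and no planned table separates these patients

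*Combined protocol and SAP*

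**What the plan says.** Section 3.1 sets the objective: "The MIMICS-3D Study will evaluate safety, effectiveness and device performance" in a real-world population.

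Section 6.3 leaves adjunctive treatment open: "All procedures should be conducted in accordance with site standard of care and patient needs, there are no prohibited concomitant treatments". The next sentence limits only how the study stent itself is used: "BioMimics 3D stent deployment shall be conducted in accordance with the IFU". The same section lists the data to be collected, including the location, size and lot number of stents, and "Post-stenting treatment".

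Section 4.2 gives the endpoint: "Acute technical success defined as the achievement of a final residual diameter stenosis <30% at the end of the procedure". The Protocol Summary and Section 12.0 repeat it with a threshold of at most 30% rather than below 30%. That difference needs reconciling but does not affect this point. Acute procedural success adds the absence of named events within 72 hours: death, stroke, MI, acute limb ischaemia, graft or treated-segment thrombosis, and urgent or emergent vascular surgery.

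Under Section 9.1 the mITT set "includes all enrolled subjects in whom the BioMimics 3D Stent System is implanted", and it is the primary set for all endpoints. The Per-Protocol set also requires eligibility and no major protocol deviation. Section 10.13 lists the major deviations: eligibility, consent, safety reporting and *unauthorised device use*. The last term is not defined.

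**The concern.** The endpoint describes the state of the lesion when the procedure ends, whichever device produced it. Suppose the study stent leaves an inadequate result or an uncovered dissection, and the operator places another manufacturer's stent or stent-graft in the same lesion. If the final angiogram is acceptable, the patient enters the numerator exactly like a patient treated with the study stent alone.

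The situation is foreseeable: Section 8.1 lists malpositioning that requires further stenting among the known complications. Section 9.1 promises a description of patients whose procedure was aborted without a stent. Nothing equivalent is planned for patients in whom the study stent was implanted and then rescued.

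At stake is how the acute-success figures can be read. Device performance is a stated objective, and Section 11.4 allows the sponsor to use results for marketing. As planned, a reader of the technical-success rate cannot tell whether the study stent achieved the result or another device did.

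**Working it through.** **Tracing one patient through the plan.** The study stent is implanted, a non-study stent is added to the same lesion in the same session, and final residual stenosis is within the threshold.

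| Rule | Section | Outcome for this patient |
|---|---|---|
| Concomitant treatment | 6.3 | Permitted |
| Acute technical success | 4.2, 12.0 | Success; the criterion does not refer to which device achieved it |
| Acute procedural success | 4.2, 12.0 | Success unless a listed 72-hour event occurs; added stenting is not listed |
| mITT | 9.1 | Included, because the study stent is implanted |
| Per-Protocol | 9.1, 10.13 | Probably included; depends on an undefined term |
| Separate row or count | 9.4 | None planned |

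**The plan's own figures.** There is none for technical success. The interval widths in Section 9.6 concern the primary endpoints. They reproduce: for example, at 75% with 500 less 10% = 450 patients, 2 × 1.96 × √(0.75 × 0.25 / 450) = 8.0%. They neither support nor weaken this point.

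**Size.** Let *s* be the technical-success rate as defined, *b* the share of all patients given a non-study stent in the target lesion, and *f* the fraction of those who end within the threshold. Counting them as failures gives *s* − *b* × *f*. The change is never upward and is at most *b*.

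The documents give none of these three values. For illustration I assume *s* = 98%, *f* = 1 and *n* = 500 (the minimum enrolment; mITT could be slightly smaller). The 95% intervals use Agresti-Coull, borrowed from Section 9.3:

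p̃ = (x + z²/2) / (n + z²), interval p̃ ± z√(p̃(1 − p̃) / (n + z²)), with z = 1.96.

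For x = 490: p̃ = (490 + 1.92) / 503.84 = 0.9763, and the half-width is 1.96 × √(0.9763 × 0.0237 / 503.84) = 0.0133.

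| Assumed *b* | Successes | Rate | 95% interval |
|---|---|---|---|
| 0 (as defined) | 490 | 98% | 96.3–99.0% |
| 1% | 485 | 97% | 95.1–98.2% |
| 2% | 480 | 96% | 93.9–97.4% |
| 5% | 465 | 93% | 90.4–95.0% |
| 10% | 440 | 88% | 84.8–90.6% |

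The 2- to 10-point gap is simply the assumed 2% to 10% bail-out rate. The table shows what such a rate would do; it is not evidence that the rate is of that order. Whether the intervals overlap is also not a test, because both rates come from the same patients.

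For procedural success the change is no larger than for technical success, since some rescued patients already fail through a listed 72-hour event.

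**The case against.** The strongest reply is that this is a descriptive, real-world study with deliberately unrestricted co-treatment, and that technical success is a secondary, procedure-level endpoint the text never attributes to one device. Nor is rescue hidden. Stents and post-stenting treatment are recorded (6.3), device failures and performance issues must be reported promptly (7.2.3), operator assessment is a secondary endpoint (4.2), and the events committee adjudicates potentially device-related events (10.15). All of this stands, and it limits the weight of the point. But no rule links any of these data to the success endpoints, and the listed stent fields do not include manufacturer. The missing piece is an analysis row.

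Three stronger readings are tempting, and the documents do not support them.

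- *Rescued patients certainly remain in Per-Protocol.* This is the likelier reading, because 6.3 permits any concomitant treatment. It is not certain: *unauthorised device use* is a major deviation without a definition, deployment must follow the IFU, and the IFU text is not reproduced in Appendix A.
- *Every rescue counts as success throughout.* Procedural success already fails when the rescue goes with treated-segment thrombosis, acute limb ischaemia, urgent surgery or another listed event.
- *The primary effectiveness result is biased in the device's favour.* A same-session added stent would not normally meet the CDTLR definition in 12.0, which needs recurrent symptoms and new ischaemic signs. Later CDTLR in such a lesion reflects two devices, and the direction of any effect is unknown.

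A reader might also infer that rescued patients should be removed from Per-Protocol to give a cleaner device result. That would select on something that happens during the procedure: cases where the study stent gave a poor acute result would leave the set and the good ones would stay.

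**Conclusion.** The point holds for acute technical success, and for acute procedural success when no listed 72-hour event occurs. As defined, the technical-success rate can only equal or overstate what the study stent achieved alone, and no planned output shows by how much. The gap cannot exceed the share of patients given a non-study stent in the target lesion. The documents give no value for that share, so the 2 to 10 points for a 2% to 10% share are an assumption that also takes every rescue to be successful. No primary result is shown to be wrong. This is an inexpensive improvement to a secondary, descriptive analysis.

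**What to change.** Keep the mITT definitions and the primary analysis unchanged.

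1. In Section 9.4, report acute technical success and acute procedural success twice: as defined, and counting any non-study stent or stent-graft placed in the target lesion at the index procedure as failure. Give the number of such patients beside the second figure.
2. In the eCRF, record the stent manufacturer if the existing stent and post-stenting fields do not already show it.
3. Do not exclude these patients from Per-Protocol on this ground. A sentence in 9.1 or 10.13 saying that an added non-study stent does not by itself remove a patient would settle the ambiguity.

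None of this restricts what operators may do. The cost is SAP wording, one extra table row for each of the two endpoints, possibly one eCRF field, and a second figure that may be less favourable. If bail-out proves rare, the two figures will nearly coincide and the table will show it.

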### 6.4 Follow-Up

The following data will be collected at **Day 30** ( $\pm$  7 days), **Month 12** (365 days  $\pm$  30 days), **Month 24** (730 days  $\pm$  60 days) and **Month 36** (1095 days  $\pm$  60 days) post Index Procedure:

- Relevant medical history including peripheral interventions (target limb)
- Physical examination (as available)
  - Ankle Brachial Index (ABI, or TBI, if applicable)
  - Rutherford Clinical Category
- Concomitant antiplatelet and anticoagulant medication
- Imaging data including patency assessment, evidence of stent fracture
- Adverse events

### 6.5 Medications

Patients should be prescribed antiplatelet medication in accordance with site standard of care and the recommendations in the IFU.

Use of aspirin, clopidogrel and other antiplatelet and anticoagulant use will be recorded from baseline through 36 months.

### 7.0 ADVERSE EVENTS

For the purpose of this Study all potentially device-related and procedure-related adverse events, major adverse events, and all vascular adverse events in the target limb will be documented throughout the 36-month visit and reported to Sponsor via the eCRF.

The Sponsor shall review all adverse events for their relationship to the Study device(s) and/or procedures and comparative anticipated safety event rates. The Sponsor will conduct evaluations of any device-related event per standard operating procedures.

An independent Clinical Events Committee (CEC) will be responsible for systematic review and adjudication of all Major Adverse Events including death, and all potentially device- -related adverse events.

### 7.1 Adverse Event definitions

Adverse event (AE) is any untoward medical occurrence, unintended disease or injury, or untoward clinical signs in subjects, whether or not related to the investigational device or procedure. In addition, the definition of AE applies to any event with an onset during enrolment / index procedure or to any underlying diseases, present at baseline, that exacerbate in severity post study procedure. Therefore, an underlying disease that was present at the time of enrolment is not reported as an AE, but any increase in the severity of the underlying disease is to be reported as an AE. This definition includes events occurring during the follow-up period.

Adverse Device Effect (ADE) / Device-Related Adverse Event: an adverse device effect (or devicerelated adverse event) is defined as any untoward adverse effect when, in the judgment of the Investigator, the clinical event has a reasonable time sequence associated with use of the investigational device and is unlikely to be attributed to concurrent disease or other procedures or medications. It is reasonable to believe that the device directly caused or contributed to the adverse event.

NOTE 1: This definition includes adverse events resulting from insufficient or inadequate Instructions for Use, deployment, implantation, installation, or operation, or any malfunction of the investigational medical device.

NOTE 2: This definition includes any event resulting from user error or from intentional misuse of the investigational medical device.

**Procedure-Related Adverse Event**: an adverse event is considered to be procedure-related when, in the judgment of the Investigator, it is reasonable to believe that the event is associated with the assigned study procedure and is not specific to the Study device (i.e., BioMimics 3D Stent System) used. Other products, surgical techniques, or medications required specifically for the procedure are likely to have contributed to the occurrence of the event.

#### A serious adverse event is defined as an adverse event that:

• Led to death,

•

- Led to a serious deterioration in the health of the subject, that either resulted in:
  - a life-threatening illness or injury, or
  - o a permanent impairment of a body structure or a body function, or
  - o in-patient hospitalisation or prolongation of existing hospitalisation
  - medical or surgical intervention to prevent life-threatening illness or injury or permanent impairment to body structure or a body function, or
- Led to foetal distress, foetal death or a congenital abnormality or birth defect.

NOTE: Planned hospitalisation for a pre-existing condition or elective cosmetic procedures, or a procedure required by the investigational plan without serious deterioration in health, is not considered a serious adverse event.

